5.6.2 Permitted Concomitant Therapy Requiring Caution

Entrectinib is mainly eliminated through hepatic clearance and CYP3A4 plays a significant role in the biotransformation of entrectinib. Co-administration of strong or moderate CYP3A4 inhibitors and inducers should be avoided. In vitro, entrectinib exhibited potential to inhibit and induce the activities of CYP3A, and potential for inhibition of CYP2C9 and CYP2D6, which suggests a potential for interaction with other drugs metabolized by these isoforms. Because of this, entrectinib should be administered with caution with the drugs listed in Appendix 2.

In addition, since absorption of entrectinib is pH sensitive, patients using H2-receptor antagonists, proton pump inhibitors (PPIs), and/or antacids should discontinue these drugs prior to starting entrectinib. If not possible, or if after discontinuation such therapy needs to be resumed, patients should be instructed to take only H2 receptor antagonists or antacids, if possible, as the duration of action of these drugs is relatively transient compared with PPIs that have longer half-lives, and thus may be administered at safe intervals in relation to entrectinib. These medications should be taken at a time point that is not proximal to entrectinib administration (at least 3-4 hours before or after entrectinib administration).

Medications that prolong QT/QTc interval should be avoided. Subjects that require medications that prolong QT/QTc interval should be monitored closely during treatment.

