8.1 Peripheral Blood Samples

8.1.1 Plasma for Pharmacokinetics and Pharmacodynamics

In phase 1b, the pharmacokinetics (PK) and pharmacodynamics (PD) of PAC-1 will be assessed following doses administered on Days 1 and 21 of the first cycle. In phase 1b, the PK and PD of entrectinib will be assessed following the dose administered on Days 3 and 21 of the first cycle. Entrectinib will be withheld on Days 1 and 2 to allow assessment of PAC-1 PK when administered as single agent. PAC-1 will be withheld on Days 2 and 3 to allow assessment of entrectinib PK when administered as single agent on Day 3. PKs of both drugs will be assessed on Day 21 to determine effects of repeated dosing or combining of the two drugs. The PK and PD analyses will occur with each dose level.

Administration of PAC-1 on Days 1 and 21 and entrectinib on Days 3 and 21 of Cycle 1 will occur in the morning. Entrectinib administration will occur 1 hour before PAC-1 on Day 21. The dose timing on this day is being specified to accommodate a sampling schedule that minimizes the number of blood draws needed from the patient. Information on the time and number of PAC-1 and entrectinib doses received for the 96 hours prior to the dose on Day 21 will be obtained from subjects. Patients will not receive their PAC-1 dose on Days 2 and 3 of Cycle 1. The doses on these days are being held in order to accurately define the absorption and metabolism of entrectinib when administered as a single agent on Day 3. Likewise, patients will not receive their entrectinib dose on Days 1 and 2 of Cycle 1. The doses on these days are being held in order to accurately define the absorption and metabolism of PAC-1 when administered as a single agent on Day 1. Actual and nominal sample collection times will be recorded on the case report forms and sample tubes.

Sample collections will occur in the mornings on Day 1 (PAC-1 only), Day 3 (entrectinib only), and Day 21 (PAC-1 and entrectinib) of the first cycle.

- Day 1, Cycle 1: Subjects receive only PAC-1.
 - Blood samples are collected immediately prior to oral ingestion of PAC-1 and at the following time points after ingestion: 0.5, 1, 2, 3, 4, 6, 7, and 24 hours.
- Day 3, Cycle 1: Subjects receive only entrectinib.
 - Blood samples are collected immediately prior to oral ingestion of entrectinib and at the following time points after ingestion: 0.5, 1, 2, 3, 4, 6, 7, and 24 hours.
- Day 21, Cycle 1: Subjects receive both PAC-1 and entrectinib.

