8.1.1.1 Pharmacokinetic Analysis

Non-compartment analysis: Non-compartmental analysis of the PAC-1 plasma concentration-time data following doses on Days 1 and 21 for Cycle 1 for each dose level. Also on Days 3 and 21 of Cycle 1, entrectinib plasma concentration data will be performed using WinNonlin 6.3 (Pharsight, St Louis, MO) for subjects in whom complete PK profiles are obtained.

Pharmacokinetic parameters to be estimated following each dose include: 1). area under the PAC-1 plasma concentration-time curve from time 0 to 24 hours (AUC_{0-24}) for days 1 and 21, 2) area under the entrectinib plasma concentration-time curve from 0 to 24 hours (AUC_{0-24}) for Days 3 and 21, 3). area under the PAC-1 plasma concentration-time curves from time 0 to infinity ($AUC_{0-\infty}$) on Day 1 only, 4). area under the entrectinib plasma concentration-time curves from time 0 to infinity ($AUC_{0-\infty}$) on Day 3 only, maximum PAC-1 and entrectinib plasma concentrations (C_{max}), 5). terminal elimination rate constant for both drugs (λ_z), and 6). oral clearance (CL/F) for both drugs.

Statistical Analysis: The influence of multiple dosing (e.g., PAC-1 Day 1 $AUC_{0-\infty}$ vs. Day 21 AUC_{0-24} and entrectinib Day 3 $AUC_{0-\infty}$ vs. Day 21 AUC_{0-24}), concurrent administration of PAC-1 and dose on the pharmacokinetics of entrectinib (e.g., Day 3 $AUC_{0-\infty}$ vs. Day 21 AUC_{0-24}), and concurrent administration of entrectinib and dose on the pharmacokinetics of PAC-1 (e.g., Day 1 $AUC_{0-\infty}$ vs. Day 21 AUC_{0-24}), will be evaluated using a generalized linear models approach. PAC-1 AUC_{0-24} , $AUC_{0-\infty}$, C_{max} and CL/F will be log transformed before statistical analysis. Entrectinib AUC_{0-24} , $AUC_{0-\infty}$, C_{max} and CL/F will be log transformed before statistical analysis. Geometric means will be calculated for the parameters on each study day. The 90% confidence intervals for the geometric mean ratios will be constructed for every comparison.

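### The PK analysis uses one contrast per drug for two effects, so multiple dosing and drug interaction cannot be separated

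*Combined protocol and SAP*

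**What the plan says.** The statistical paragraph of Section 8.1.1.1 lists three influences on the pharmacokinetics and gives an example contrast for each.

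- Multiple dosing: "Statistical Analysis: The influence of multiple dosing (e.g., PAC-1 Day 1" AUC0-∞ against Day 21 AUC0-24, and for entrectinib Day 3 AUC0-∞ against Day 21 AUC0-24.
- PAC-1 acting on entrectinib: "concurrent administration of PAC-1 and dose on the pharmacokinetics of entrectinib (e.g., Day 3" AUC0-∞ against Day 21 AUC0-24.
- Entrectinib acting on PAC-1: "concurrent administration of entrectinib and dose on the pharmacokinetics of PAC-1 (e.g., Day 1" AUC0-∞ against Day 21 AUC0-24.

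All of these "will be evaluated using a generalized linear models approach" on log-transformed parameters, and "The 90% confidence intervals for the geometric mean ratios will be constructed for every comparison". The model terms and their coding are not given.

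Section 8.1.1 fixes the sampling, all of it within Cycle 1: "Sample collections will occur in the mornings on Day 1 (PAC-1 only), Day 3 (entrectinib only), and Day 21 (PAC-1 and entrectinib) of the first". It describes the last day as serving both purposes: "PKs of both drugs will be assessed on Day 21 to determine effects of repeated dosing or combining of the two drugs". Under Section 5.1, Cycle 1 PAC-1 is given on Day 1 and Days 4 to 21, and entrectinib on Days 3 to 28. Objective 2.3 and the synopsis list single dosing, repeated dosing and combination for each drug.

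**The concern.** Two differently named effects are assigned the same pair of days and the same pair of AUCs. An analyst who follows the text would produce one geometric mean ratio per drug and report it, with the same 90% interval, once as the multiple-dosing effect and once as the interaction effect. A change caused by one could be credited to the other, and effects in opposite directions could hide each other. The ratio would then be open to being read as a drug-interaction finding for a combination in which each drug is being characterised alongside the other.

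**Working it through.** The plan states no sample size, power or error rate for the PK comparison, so there is no figure to reproduce. The question is whether the planned days identify the effects.

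**1. States that are sampled (Sections 5.1 and 8.1.1)**

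| Drug | Day | Repeated dosing | Partner drug |
|---|---|---|---|
| PAC-1 | 1 | no | no |
| PAC-1 | 21 | yes | yes |
| Entrectinib | 3 | no | no |
| Entrectinib | 21 | yes | yes |

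Neither drug is sampled after repeated dosing without its partner, or after a single dose with it. Entrectinib does continue without PAC-1 on Days 22 to 28, but no PK profile is scheduled then.

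**2. Rank of the model.** Take log(parameter) = baseline + repeated dosing + co-administration.

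- Intercept and two effects: rank 2 for 3 parameters, because the two effect columns are identical.
- Nine patient effects (3 + 6 patients, Section 12.3) and two effects: rank 10 for 11 parameters.
- Dose level and its interactions with both effects: rank 4 for 6 parameters.

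More patients would not change this. AUC0-24, Cmax and CL/F come from the same days, so the fact that the contrasts are given as examples does not help.

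**3. What the data show.** The observed ratio is the multiple-dosing ratio times the interaction ratio. The pairs (1.5, 1.0), (1.0, 1.5), (0.75, 2.0) and (2.0, 0.75) are arbitrary, and each gives 1.5.

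**4. Using dose as a covariate.** The plan does name dose as a factor. For entrectinib, suppose the interaction is linear in PAC-1 dose on the log scale. Let D(d) be the mean log ratio at PAC-1 dose d, so D(d) = a + b·d, where a is the repeated-dosing effect. Then

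- b = [D(750) − D(625)]/125
- a = D(625) − 625b = 6·D(625) − 5·D(750)

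With s the SD of a patient's log ratio:

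- 3 + 6 patients: SE(a) = s·√(36/3 + 25/6) = 4.02s
- 6 + 6 patients: SE(a) = s·√(36/6 + 25/6) = 3.19s

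The documents give no within-patient CV. Assuming 20 to 40%, s = √2·√ln(1 + CV²) = 0.280 to 0.545. The 90% limits, as a factor either way, are:

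| Patients | Repeated-dosing effect via dose term | Net ratio |
|---|---|---|
| 3 + 6 | 8.4 to 63 | 1.19 to 1.40 |
| 6 + 6 | 5.1 to 23 | 1.16 to 1.33 |

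For PAC-1 this route is closed at levels 1 and 2, where entrectinib is 600 mg at both.

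**5. Timing of the entrectinib dose on Day 21.** Section 5.3.1 has entrectinib taken in the evening, but in the morning on Days 3 and 21. The dose before the Day 21 profile may therefore be about 12 h earlier. In a one-compartment linear model with no true effect of either kind,

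Day 21 AUC0-24 / Day 3 AUC0-∞ = 1 + e^(−12k) − e^(−24k).

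The half-life is not in the documents. For assumed values of 6, 12, 20, 30 and 40 h the ratio is 1.19, 1.25, 1.22, 1.18 and 1.15.

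**The case against.** The best defence is that the AUC pair was not chosen at random. With linear, time-invariant PK at steady state, single-dose AUC0-∞ equals AUC0-24 over a regular dosing interval, so the ratio could be read as interaction alone. That is a legitimate reading if it is declared. The plan does not declare it, these data cannot test it, and it sets to zero the multiple-dosing effect that the same paragraph says will be evaluated. It would not serve Cmax, which can rise through accumulation under linear PK. For entrectinib the irregular Day 21 interval also breaks the equality.

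A second defence is that Section 8.1.1 speaks of repeated dosing or combining, and that objective 2.3 can be read as single dose alone followed by repeated dosing in combination, which the design does deliver. That stands. The claim to separate effects rests mainly on one paragraph of Section 8.1.1.1.

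A third is that the plan fixes no model, so strict collinearity depends on the coding. This is formally right, as the dose term shows for entrectinib. A similar route for PAC-1 would need dose level −1 to open (entrectinib 400 and 600 mg). Either route relies on a straight line extrapolated to zero dose, which two dose points cannot test.

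A reader might infer that the PK comparison yields nothing usable. The documents do not support that, because the net ratio is estimable with ordinary precision. A reader might also take Section 5.6.2, "In vitro, entrectinib exhibited potential to inhibit and induce the activities of CYP3A", as showing that repeated entrectinib changes its own exposure. The section reports in vitro potential and draws from it a caution about other drugs. Self-interaction is an inference, for entrectinib only; the documents give no metabolic route for PAC-1.

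**Conclusion.** Wrong as written, and minor. For each drug the plan supports one ratio, repeated dosing plus co-administration against a single dose alone, and not the two effects it names. This follows from the sampling days and needs no outside figure. Only the precision of the dose-term route and the size of the timing shift rest on assumed values (CV 20 to 40%, half-life 6 to 40 h).

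It would go too far to say that dose selection or the trial's main conclusions are at risk. The PK objective is exploratory and limited to Phase 1b, with 9 to 12 patients (Section 12.3.1), and Section 8 makes the correlative analyses dependent on funding. The MTD is defined by DLTs and Phase 2 by 3-month PFS, and no decision rule uses a PK ratio.

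**What to change.** In Section 8.1.1.1, replace the multiple-dosing and interaction analyses with one pre-specified contrast per drug: log Day 21 AUC0-24 minus log single-dose AUC0-∞ (Day 1 for PAC-1, Day 3 for entrectinib), paired within patient and reported as a geometric mean ratio with a 90% CI. Handle the Cmax ratio likewise. Label the result as the net effect of repeated dosing plus co-administration. Remove the claims to estimate the two effects separately, and align the Day 21 sentence in Section 8.1.1, objective 2.3 and the synopsis.

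If the sponsor wishes to read the AUC ratio as interaction alone, state the assumption (linear, time-invariant PK at steady state) and say that these data cannot test it.

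Add as a limitation that the entrectinib dose moves from evening to morning on Day 21, so that Day 21 AUC0-24 is not a regular dosing interval.

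The cost is a wording amendment to the combined protocol and SAP and a narrower stated exploratory objective. Doses, visits and samples stay as they are.

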8.1.1.2 Pharmacodynamic Assessment

The pharmacodynamic (PD) effects of PAC-1 (Days 1 and 21 of Cycle 1), and entrectinib (Days 3 and 21 of Cycle 1), may be used to assess the systemic responses of individuals following PAC-1 or entrectinib doses administered orally. Systemic variables are defined as plasma concentrations of PAC-1 or entrectinib, which will be measured and used to assess whether PAC-1 or entrectinib has affected the production of these biological markers. Measures of toxicity (e.g., changes in WBC counts, differential cell populations, platelets, etc.) are also considered systemic PD variables.

8.1.2 Mechanisms of Action Analysis

Subject consent will be obtained for collection of peripheral blood samples for whole blood, plasma and serum prior to treatment on Cycle 1 Day 1, Cycle 2 Day 1 and at progression (safety visit). This specimen will be used for analysis related to Mechanisms of Action.

8.1.3 Circulating Tumor Cells (CTCs)

Subject consent will be obtained for collection of peripheral blood samples prior to treatment on Cycle 1 Day 1, Cycle 2 Day 1 and at progression (safety visit). This specimen will be analyzed for total CTCs. Spearman correlation will be computed using PROC CORR in SAS (Cary, NC). CTC number or change from Cycle Day 1 to Cycle 2 Day 1 will be correlated with ORR assessed by imaging (revised RECIST 1.1 criteria). Spearman correlation will be computed using PROC CORR in SAS (Cary, NC).

8.1.4 Somatic Baseline

Whole blood will be collected prior to treatment Cycle 1 Day 1 for somatic baseline testing.

8.1.5 Plasma for ctDNA

Subject consent will be obtained for collection of peripheral blood samples for ctDNA prior to treatment on Cycle 1 Day 1, Cycle 2 Day 1 and at progression (safety visit).

8.2 Tissue Samples

8.2.1 Archival or Fresh Tissue

Archival tumor tissue (metastatic disease preferred) is required if available and should be identified at screening and shipped by Cycle 1 Day 1. If archival tissue is not available, a biopsy is required prior to Cycle 1 Day 1 of treatment. There is a cap of 15 biopsies.

8.2.2 Immunohistochemistry (IHC)

IHC for markers such as but not limited to procaspase 3. Determine correlation between procaspase 3 expression in tumor tissue and clinical **response**. Procaspase 3 expression will be correlated with ORR assessed by imaging (revised RECIST 1.1 criteria). Spearman correlation will be computed using PROC CORR in SAS (Cary, NC).

8.2.3 Imaging

Imaging may also be performed in an effort to elucidate aspects of the mechanism of action.

8.2.4 Genomic Analysis

Genomic analysis may also be performed in an effort to elucidate aspects of the mechanism of action.

8.3 Confidentiality of Biospecimens

Samples that are collected will be identified by a subject's study number assigned at the time of registration to the trial. Any material issued to collaborating researchers will be anonymized and only identified by the subject's study number.

8.4 Storage of Biospecimens

Remaining specimens once protocol described biospecimen-based studies are complete will be stored for future unspecified cancer related research after consent is obtained from subjects.

9. CRITERIA FOR DISEASE EVALUATION

Tumor response will be defined by the Response Evaluation Criteria in Solid Tumors (RECIST) Version 1.1.²¹

9.1 Measurable Disease

The presence of at least one measurable lesion. If the measurable disease is restricted to a solitary lesion, its neoplastic nature should be confirmed by cytology/histology.

9.2 Measurable Lesions

Measurable lesions are defined as the presence of at least one measurable lesion. Measurable lesions are defined as those that can be accurately measured in at least one dimension (longest diameter to be recorded) as ≥ 20 mm by chest x-ray, as ≥ 10 mm with CT scan, or ≥ 10 mm with calipers by clinical exam. All tumor measurements must be recorded in millimeters (or decimal fractions of centimeters).

9.3 Non-measurable Lesions

All other lesions (or sites of disease), including small lesions (longest diameter < 10 mm or pathological lymph nodes with ≥ 10 to < 15 mm short axis), are considered non-measurable disease. Bone lesions, leptomeningeal disease, ascites, pleural/pericardial effusions, lymphangitis cutis/pulmonitis, inflammatory breast disease, and abdominal masses (not followed by CT or MRI), are considered as non-measurable.

NOTE: Cystic lesions that meet the criteria for radiographically defined simple cysts should not be considered as malignant lesions (neither measurable nor non-measurable) since they are, by definition, simple cysts. ‘Cystic lesions’ thought to represent cystic metastases can be considered as measurable lesions, if they meet the definition of measurability described above. However, if non-cystic lesions are present in the same subject, these are preferred for selection as target lesions.

9.4 Target Lesions

All measurable lesions up to a maximum of 2 lesions per organ and 5 lesions in total, representative of all involved organs, should be identified as **target lesions** and recorded and measured at baseline. Target lesions should be selected on the basis of their size (lesions with the longest diameter), be representative of all involved organs, but in addition should be those that lend themselves to reproducible repeated measurements. It may be the case that, on occasion, the largest lesion does not lend itself to reproducible measurement in which circumstance the next largest lesion which can be measured reproducibly should be selected. A sum of the diameters (longest for non-nodal lesions, short axis for nodal lesions) for all target lesions will be calculated and reported as the baseline sum diameters. If lymph nodes are to be included in the sum, then only the short axis is added into the sum. The baseline sum diameters will be used as reference to further characterize any objective tumor regression in the measurable dimension of the disease.

9.5 Non-target Lesions

All other lesions (or sites of disease) including any measurable lesions over and above the 5 target lesions should be identified as non-target lesions and should also be recorded at baseline. Measurements of these lesions are not required, but the presence, absence, or in rare cases unequivocal progression of each should be noted throughout follow-up.

9.6 Evaluation of Target Lesions

NOTE: Please see the international criteria proposed by the Response Evaluation Criteria in Solid Tumors (RECIST) Committee, version 1.1 (Eur J Cancer 45;2009:228-247) for special notes on the assessment of target lesions.

Complete Response (CR)	Disappearance of all target lesions. Any pathological lymph nodes (whether target or non-target) must have reduction in short axis to <10 mm.
Partial Response (PR)	At least a 30% decrease in the sum of the diameters of target lesions, taking as reference the baseline sum diameters
Progressive Disease (PD)	At least a 20% increase in the sum of the diameters of target lesions, taking as reference the smallest sum on study (this includes the baseline sum if that is the smallest on study). In addition to the relative increase of 20%, the sum must also demonstrate an absolute increase of at least 5 mm. (Note: the appearance of one or more new lesions is also considered progressions).
Stable Disease (SD)	Neither sufficient shrinkage to qualify for PR nor sufficient increase to qualify for PD, taking as reference the smallest sum diameters while on study

9.7 Evaluation of Non-target Lesions

Complete Response (CR)	Disappearance of all non-target lesions and normalization of tumor marker level.
Incomplete Response/Stable Disease	Persistence of one or more non-target lesion(s) and/or maintenance of tumor marker level above the normal limits
Progressive Disease (PD)	Appearance of one or more new lesions and/or unequivocal progression of existing non-target lesions.

Although a clear progression of “non-target” lesions only is exceptional, the opinion of the site investigator should prevail in such circumstances, and the progression status should be confirmed at a later time by the sponsor-investigator.

9.8 Evaluation of Best Overall Response

NOTE: Revise table if response rate is primary objective of the study, and confirmation of response is required. See Eur J Cancer 45;2009:228-247 for complete details.

Target Lesions	Non-Target Lesions	New Lesions	Overall Response**
CR	CR	No	CR
CR	Non-CR/ Non-PD	No	PR
CR	Not evaluated	No	PR
PR	Non-PD/ or not all evaluated	No	PR
SD	Non-PD or not all evaluated	No	SD
Not all evaluated	Non-PD	No	Non-evaluable
PD	Any	Yes or No	PD
Any	PD*	Yes or No	PD
Any	Any	Yes	PD

In exceptional circumstances, unequivocal progression in non-target lesions may be accepted as disease progression.
All responses will require confirmation with repeat imaging or physical exam at \geq 4 weeks.

Subjects with a global deterioration of health status requiring discontinuation of treatment without objective evidence of disease progression at that time should be classified as having “symptomatic deterioration.” Every effort should be made to document the objective progression even after discontinuation of treatment.

In some circumstances, it may be difficult to distinguish residual disease from normal tissue. When the evaluation of complete response depends on this determination, it is recommended that the residual lesion be investigated (fine needle aspirate/biopsy) to confirm the complete response status.

